## **Interim analyses**

No interim analyses are planned, since there are no anticipated problems that are detrimental to the participants, as all topical drugs prescribed in the trial are well-known manufactured drugs.

Criteria for formally halting the trial will be when the last patient visit has taken place.

## **Methods for additional analyses (e.g., subgroup analyses)**

Subgroup analyses of the primary and secondary outcomes by interaction terms in regression models are planned, to investigate if the dermatology nurses or the percentage of nurse-contacts made by telephone affect the intervention.

## **Analysis methods to handle protocol non-adherence and any statistical methods to handle missing data**

Missing data on the primary outcome will be evaluated to assess the occurrence of specific missing data patterns, and if necessary, missing data will be handled by using multiple imputation. Missing effectiveness values are imputed at missing time points using values from available time points. Furthermore, missing data will not be imputed for PRO outcomes or adherence measures.

## **Plans to give access to the full protocol, participant level-data and statistical code**

Access to the full dataset (participant-level dataset and statistical code) obtained in the clinical trial is not planned. The datasets analysed during the current study are available from the corresponding author on reasonable request. After the end of the study and after the reports have been submitted and approved by the authorities (the Committee on Health Research Ethics), the sponsor will ensure the study data are deleted.

## **Supervision and monitoring**

### **Composition of the coordinating centre and trial steering committee**

There is no trial steering committee.

The coordinating centre is responsible for overall data management, monitoring and communication at the study site and among the researchers, and general supervision of the conduct of the research project.

The composition of the coordinating centre is as follows:

- Principal investigator: MTS
  - Design and conduct of the study
  - Administration of research grants
  - Handling cooperative agreements
  - Drafting contracts in compliance with applicable laws and regulations
  - Publication of study reports
  - Preparation of protocol and revisions and case report forms
  - Recruitment of participants
- Sponsor: KEA
  - Design and conduct of the study
  - Publication of study reports
  - Preparation of protocol and revisions
  - Recruitment of participants
- Three dermatology nurses
  - Supporting the principal investigator during patient consultations and providing the study intervention
- Two blinded assessors
  - Measuring severity of psoriasis (primary outcome) and weighing study medication

## **Composition of the data monitoring committee, its role and reporting structure**

To the best of our knowledge, the patient supporting intervention delivered by dermatology nurses in itself does not carry any risks for participants. Therefore, a data monitoring committee is not required. The study is a smaller-size study without critical safety concerns and addresses less-essential outcomes (relief of symptoms and adherence to medication). The Danish Medicines Agency was consulted and concluded the study was not a pharmaceutical trial and, furthermore, a data monitoring committee was not needed to audit the trial.

The principal investigator and sponsor guarantee data and participant safety.

## **Adverse event reporting and harms**

PRO data will not be monitored during the study for the purposes of providing information about the clinical care of individual trial participants, since patients' awareness of any fluctuations may impact on the study outcomes. Screening for AEs will be conducted at baseline and weeks 12, 24, 36 and 48. At each visit, the investigator will systematically screen for all known side effects listed in the product summary for prescribed topical drugs both by interviewing the participants, inspecting the skin surface and by reading through all files in the patient chart. The investigator will adhere to instructions for post marketing reporting of adverse drug experiences. Furthermore, a table with all AEs will be published along with study outcomes according to instructions for reporting adverse events (AEs), SAEs, serious adverse reactions (SARs), and suspected unexpected serious adverse reactions (SUSARs). A table summarizing the number of adverse events in the non-intervention vs. intervention group will be used to compare if there are any group-related differences in terms of AEs, and to investigate any potential increased use of topical drugs if one of the groups is associated with an increased risk of AEs.

A table summarizing number of adverse events in the non-intervention vs. intervention group will be used to compare if there are any differences between the groups in regard to AEs and to investigate if any increased use of topical drugs in one of the groups is associated with an increased risk of AEs.

If there is a suspicion of a SAE, the study investigator must immediately be contacted, arrange for relevant inquiries, ensure SAE reporting, and assess if the participant should cease participating in the trial.

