## **Trial design**

The study is a randomized, controlled, investigator-initiated, parallel group with 1:1 allocation ratio, superiority trial (RCT) with an intention to treat (ITT) analysis.

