## **Recruitment**

The Dermatology Department will be the primary recruitment and trial site until the maximum planned number of 115 psoriasis patients has been included. Supplemental patient recruitment may be used by contact with dermatologists in practice or by advertisements in local newspapers, at public institutions or social media on the internet.

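### Adverse events are compared by number of events, although the stated question is about risk; patients with at least one new event should be the compared quantity

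*Combined protocol and SAP*

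**What the plan says.** All of the relevant text is in the section Adverse event reporting and harms.

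- **Measure.** The comparison is stated twice in nearly the same words: "A table summarizing the number of adverse events in the non-intervention vs. intervention group will be used to compare" and, in the next paragraph, "A table summarizing number of adverse events in the non-intervention vs. intervention group will be used to compare if there are any differences".
- **Purpose.** The second statement adds that the table is meant "to investigate if any increased use of topical drugs in one of the groups is associated with an increased risk of AEs".
- **Collection.** "Screening for AEs will be conducted at baseline and weeks 12, 24, 36 and 48". The list is checked in full each time: "At each visit, the investigator will systematically screen for all known side effects listed in the product summary for prescribed topical drugs". The methods are interview, skin inspection and chart reading.
- **Other output.** In addition, "a table with all AEs will be published along with study outcomes according to instructions for reporting adverse events". No counting unit is named there.

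The statistical sections, from the primary and secondary outcome analyses through to missing data, do not cover AEs. The text on actions after a serious AE, the annual report to the ethics committee (Frequency and plans for auditing trial conduct) and Economic evaluation mention AEs or serious AEs but give no counting rule. No section gives a patient-level AE count, a rule for an event that continues from one visit to the next, or a test or interval for AEs.

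**The concern.** The measure does not match the question. Risk is a proportion of patients, and a count of events is not. Ten events may be ten patients once each or three patients several times, and the stated table cannot tell these apart.

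The way AEs are collected makes this matter more. Because the whole list is checked again at each visit, a lasting local effect meets the screening criterion every time it is still present. Without a rule for continuing events, the total can reflect how long effects last and how early they are found, as well as how many patients have them.

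This is the only between-arm safety comparison that the plan describes, and it is aimed at a plausible harm: more support, hence more drug use, hence more side effects. The count could suggest such a difference where equal numbers of patients are affected, or mask one where the numbers differ.

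**Working it through.** The plan gives no figure for the AE comparison, so there is none to reproduce. The check is arithmetic on the counting rule.

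**Inputs from the document**
- Planned size: recruitment runs "until the maximum planned number of 115 psoriasis patients has been included" (Recruitment). With 1:1 allocation (Trial design) that is about 58 and 57 patients.
- Screens after baseline: weeks 12, 24, 36 and 48, so 4.

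**Inputs assumed, because the document gives no AE rates**
- 10 patients in each arm have one side effect each.
- In one arm, k of these 10 have an effect that is found at week 12, lasts to week 48 and is recorded at every visit.
- All other affected patients contribute one record.

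**Formula.** Events in that arm = (10 − k) × 1 + k × 4 = 10 + 3k. Events in the other arm = 10. Patients affected = 10 in each arm, whatever k is.

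| k | Events | Ratio | Patients affected |
|---|---|---|---|
| 0 | 10 vs 10 | 1.0 | 10 vs 10 |
| 1 | 13 vs 10 | 1.3 | 10 vs 10 |
| 2 | 16 vs 10 | 1.6 | 10 vs 10 |
| 3 | 19 vs 10 | 1.9 | 10 vs 10 |
| 4 | 22 vs 10 | 2.2 | 10 vs 10 |
| 5 | 25 vs 10 | 2.5 | 10 vs 10 |

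**The same data at patient level.** 10/58 = 17.2% and 10/57 = 17.5%. The risk difference is −0.3 percentage points. Its standard error is √(0.1724 × 0.8276/58 + 0.1754 × 0.8246/57) = 0.0707, so the 95% CI is −0.3 ± 1.96 × 7.07, or about −14.2 to 13.6 points. This shows no difference, and also how imprecise one overall contrast is at this size.

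**The opposite direction.** Suppose one arm has 10 affected patients with k = 2, giving 16 events, and the other has 16 patients with one event each, also 16 events. The event table shows no difference, although 10/58 = 17.2% and 16/57 = 28.1% of patients are affected.

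**The case against.** The strongest reply is that repeat counting is inferred. The document sets occasions for screening and does not say that each detection becomes a new event. Many readers would take the number of AEs to mean distinct events, and the AE form, which is not in the document, may already merge continuing ones. This stands: the text permits repeat counting but does not say that it will happen. The mismatch between a count and a risk remains even if every event is counted once, because one patient can have several distinct events.

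Four stronger readings are tempting, and the document does not support them.

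- **The safety comparison has an inflated false-positive rate.** In a simulation with no true difference (assumed 10–30% of patients affected, first detection spread over the four visits), treating records as independent gave p<0.05 in 14–17% of trials if half of the effects last and 18–22% if all last. A patient-level Fisher test gave 3–4%. The plan specifies a table and no test, so these rates belong to an analysis that nobody plans.
- **One or two patients can decide the result.** In the table above they move the count only to 13 or 16 vs 10.
- **Findings at baseline contaminate the comparison.** Nothing says that they enter it. A baseline screen is the natural reference for what is new, especially as patients already attending the clinic may be included (Study setting).
- **The count is the only safety output.** The section also promises a published table of all AEs, although without a counting unit.

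It is also fair to say that intervals for every side effect would add many imprecise contrasts in a trial of 115 patients. The fix below avoids that.

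**Conclusion.** The point holds as a cheap improvement to the safety table. The stated measure cannot answer the stated question about risk, and the absence of a rule for continuing events leaves room for one lasting effect to count up to four times after baseline. Under the assumed rates, four such patients in one arm produce an apparent ratio of 2.2 with equal numbers of patients affected.

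The size rests on assumed AE frequency and persistence, on detection at week 12, and on each detection being recorded as an event, none of which the document settles. It describes how a descriptive table could look. It does not show that the trial's safety conclusion will be wrong, and it has no bearing on the efficacy analyses.

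**What to change.** In Adverse event reporting and harms, replace the two near-identical sentences with one specification:

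- The compared quantity is the number and percentage of patients in each arm with at least one new AE after baseline, with one overall risk difference and 95% CI.
- Patient counts by side effect are given descriptively, without intervals.
- Event counts stay as a second column, and a continuing event is counted once.
- The baseline screen is the reference for deciding what is new.

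The cost is a rewritten table specification and a new/continuing flag on the AE form, if the form does not already have one. The downside is slightly more coding at each visit, and repeat events weigh less in the main comparison. Keeping the event column preserves that information.

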## **Frequency and plans for auditing trial conduct**

At all times, the investigator will provide direct access to monitoring, auditing and/or inspection by the Committee on Health Research Ethics, the regional Data Protection Agency, national health authorities or health authorities from other countries. This auditing will be independent of the investigator and the sponsor. The investigator will allow the authorities (and the Committee on Health Research Ethics) access to monitor and quality check the data. Furthermore, the investigator will provide an annual report to the regional Committee on Health Research Ethics reporting any adverse events occurring during the trial period.

All data used in the analysis will be stored in REDCap, OPEN Analyze or Scientific Services at The Danish Health Data Authority.

## **Plans for communicating important protocol amendments to relevant parties (e.g.,**

## **trial participants, ethical committees)**

Important protocol amendments will be reported to the relevant parties (i.e., the Regional Committees on Health Ethics for Southern Denmark, Denmark, the trial participants, and trial registries) by e-mail. Substantial amendments are only implemented after approval of the Regional Committees on Health Ethics for Southern Denmark, Denmark. All non-substantial amendments are communicated to the Regional Committees on Health Ethics for Southern Denmark, Denmark and within the Annual Safety Report.

## **Economic evaluation**

To assess the effectiveness of the intervention a cost-effectiveness/utility analysis will be performed. The effect measures are Quality adjusted life years (QALY), DLQI and LS-PGA. EQ-5D values (based on danish societal weights) (43) will be used to calculate QALYs (44). The intervention has numerous potential short-term economic benefits within the study period, primarily a reduction of the need for prescribing narrow-band ultraviolet B (UVB) treatment, biologic treatment, systemic antipsoriatic drugs and laboratory analyses used to monitor the use of drugs. Furthermore, the intervention may reduce patients' need for consulting the general practitioner or private dermatologists to obtain a prescription for antipsoriatic treatment. As the intervention may improve patients' well-being, there is likely to be a reduced need for psychological or psychiatric treatment. The intervention is not expected to reduce the incidence of other psoriasis co-morbidities, except for improved well-being. Adverse events will be recorded but not included in the economic evaluation model, as they are assumed to be mild for both groups, thus not incurring relevant costs. Costs and resources will be calculated from a healthcare sector perspective including healthcare system costs. The total healthcare costs (measured in GBP in 2021 prices) for participants will be obtained to compare costs for the intervention group and non-intervention. Cost data for the economic evaluation will be compiled by i) registration at each outpatient visit during the trial period of the time spent by the nurse delivering dermatology support to patients in the intervention group (study personnel will receive a fixed payment per work hour), ii) registration of cost for drugs delivered free-of-charge (by searching the patient medical charts, estimating drugs linked to a unique pharmaceutical item number (45), and iii) extraction of data from the Danish Health registries to compile total healthcare costs, linked to participants' personal identification number, in a two-year period prior to inclusion in the study and during the study period (48 weeks). Data from the Danish Health registries contain real-life

pseudonymized individual-level data for study participants. Data will be collected by Scientific Service (Danish: Forskerservice) at The Danish Health Data Authority via joint port access (46) linked with study data using the civil registration number. All analyses will be conducted on Scientific Service's secure server, using encrypted civil registration numbers. Data will include the total cost of prescription medication (data from The Danish National Prescription Registry (47)) and hospital procedures, including in- and outpatient treatments (data from National Patient Register (LPR (Landspatientregistret)) and the Diagnosis Related Group (DRG)-grouped National Patient Register (48)). Visits in the primary sector, including those of the general practitioner and practicing dermatologist, will be extracted from the National Health Service Register (49).

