### **Intervention description**

#### **Intervention group: Detailed description of the improved patient-support**

The intervention group will include support delivered by three experienced dermatology nurses. Each patient will be supported by the same dermatology nurse throughout the entire study period. The intervention is expected to encourage psoriasis patients to apply the topical drugs on a regular basis by 1) ensuring that patients have a reminder system (16, 17), 2) making patients accountable (18-20), 3) providing support (21), 4) building trust in the treatment and healthcare-provider (10, 13, 22, 23), and 5) by increasing perceived ease of use via favourable comparisons to other treatment options (18, 24). Participants in the intervention group will be seen by a nurse in the dermatology clinic at baseline and weeks 12, 24, 36 and 48. Furthermore, the participants will either be seen in the dermatology clinic or receive follow-up from the nurse by telephone at weeks 1, 4, 8, 16, 20, 28, 32, 40 and 44.

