**Consultation by nurse in the clinic or digital follow-ups at weeks 1, 4, 8, 16, 20, 28, 32, 40 and 44**  
(expected duration: 20 min.) (nurse): Participants choose whether they wish to meet the nurse in the clinic or be contacted via telephone, where they may ask questions regarding their treatment and receive further instructions.

**Visits at weeks 12, 24, 36 and 48** (expected duration: 30 min.). Participants are seen by the dermatologist and a nurse in the clinic, questions are answered, and adjustment of topical treatment is introduced as needed.

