#### **Data that is considered to be source data**

The following source data will be recorded from the patients' medical chart or from an interview and stored in REDCap (41): Duration of psoriasis, previous and current systemic, biologic, and topical treatment for psoriasis (in a two-year period prior to inclusion in the study) and socio-demographic data (relationship status, education and job status, municipality, and national origin). During the study, LS-PGA (including BSA) and the weight of consumed topical medication will be assessed by the blinded assessor. DLQI and EQ-5D will be reported by patients. The investigator will obtain data regarding the antipsoriatic drugs prescribed during the study period,

and the rate of filled first prescriptions for antipsoriatic drugs during the study period will be obtained. The trial personnel will note down the time used for consultations.

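### The rule for costing nurse time covers outpatient visits only, so as written it omits telephone contacts (up to 180 min per intervention patient), and its overlap with registry outpatient costs is not settled

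*Combined protocol and SAP*

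**What the plan says.** The Economic evaluation section builds cost from three sources. Item (i) is "registration at each outpatient visit during the trial period of the time spent by the nurse delivering dermatology support", for the intervention group only, with study personnel paid a fixed amount per hour worked. Item (ii) is drugs supplied free of charge. Item (iii) is "extraction of data from the Danish Health registries to compile total healthcare costs", for the two years before inclusion and the 48 study weeks. The same section says the registry data include "hospital procedures, including in- and outpatient treatments", taken from the National Patient Register and its DRG-grouped version.

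The intervention has five scheduled clinic visits (baseline and weeks 12, 24, 36 and 48) and nine contacts in between. For those nine, the detailed description of the intervention says that "the participants will either be seen in the dermatology clinic or receive follow-up from the nurse by telephone", and the description of study visits says: "Participants choose whether they wish to meet the nurse in the clinic or be contacted via telephone".

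Two other places bear on what is recorded. The source data section says: "The trial personnel will note down the time used for consultations". The section on additional analyses plans a subgroup analysis by the percentage of nurse contacts held by telephone.

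The Cost-effectiveness analyses section makes the between-group difference in total 48-week cost the numerator of the ICER.

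**The concern.** The intervention sections treat being seen in the clinic and being telephoned as alternatives. On the ordinary reading, an outpatient visit in item (i) is therefore the clinic alternative, and a telephone contact contributes no nurse time to the cost. Any such omission falls wholly on the intervention arm and lowers its cost.

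Cost-effectiveness is one of the four stated objectives, and the Discussion points to possible implementation in the clinic. The planned safeguards would not reveal the problem. Bootstrapping and acceptability curves describe sampling uncertainty in whatever costs are entered. Adjustment for costs in the previous two years cannot restore a cost that arises after randomization.

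The second question runs the other way. The trial takes place in a hospital outpatient clinic, and item (iii) adds hospital outpatient costs for the same weeks. If the registry tariff for a clinic contact already covers the nurse, item (i) would charge that time again, and only in the intervention arm, because item (i) applies only there.

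**Working it through.** The plan states no nurse-time total, unit cost or expected ICER, so there is no figure to reproduce. The check sums the scheduled minutes.

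**Inputs**
- Baseline visit, intervention: 60 min, of which physician 20 and nurse 40 (description of study visits).
- Interim contacts: 9, at weeks 1, 4, 8, 16, 20, 28, 32, 40 and 44, each 20 min with the nurse; one duration is given for both modes (same section).
- Quarterly visits, intervention: 4 of 30 min with dermatologist and nurse (same section). The nurse's share, *s*, is not stated. Assumed range: 0 to 30 min.
- Non-intervention: 20 min with the dermatologist and possibly 15 min with a nurse at baseline, then 4 visits of 15 min with the dermatologist (standard-of-care patient support section).
- *k* = number of interim contacts held by telephone, 0 to 9. No expected value is given.

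**Number of contacts:** 5 + 9 = 14, of which 9/14 may be by telephone.

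**Scheduled nurse time** = 40 + 9 × 20 + 4*s*. **Time outside item (i) as written** = 20*k*.

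| *s* (min) | Scheduled nurse time (min) | *k* = 5: omitted | *k* = 9: omitted | Left in item (i) at *k* = 9 |
|---|---|---|---|---|
| 30 | 40 + 180 + 120 = 340 | 100/340 = 29% | 180/340 = 53% | 160 min |
| 15 | 40 + 180 + 60 = 280 | 100/280 = 36% | 180/280 = 64% | 100 min |
| 0 | 40 + 180 + 0 = 220 | 100/220 = 45% | 180/220 = 82% | 40 min |

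At *k* = 0 nothing is omitted.

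**Comparison with the other arm.** Scheduled visit and contact time is 60 + 180 + 120 = 360 min in the intervention arm. In the non-intervention arm it is 20 + 60 = 80 min, or 95 min with the baseline nurse instruction. The difference is 280 or 265 min, and the interim contacts make up 180/280 = 64% or 180/265 = 68% of it. These are contact durations, not staff-minutes: a visit attended by two professionals is counted once.

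**Possible overlap with the registers.** Clinic contacts that could appear there number 5 (all interim contacts by telephone) to 14 (none by telephone) per intervention patient, against 5 per non-intervention patient. The plan does not say whether a nurse contact generates a tariff, whether a telephone contact appears in the register, or whether trial contacts are removed from item (iii). The overlap cannot be sized.

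**The case against.** The strongest reply is that the wording is loose and the data are in hand. Trial personnel are to note consultation time, with no restriction to clinic visits, and the telephone subgroup analysis requires contact mode to be recorded. Item (i) speaks of nurses supporting the intervention group at an hourly rate, which would fit costing all their hours. On this view, telephone time may well enter the cost.

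Part of this stands. A reader might infer that telephone time goes unrecorded, or that it will certainly be missing from the analysis; the documents support neither. What they do not contain is any statement that the time log feeds the cost calculation, and the subgroup analysis needs only the percentage of contacts by telephone, not their minutes. The costing rule itself names outpatient visits, and an analyst who follows it omits the calls.

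A reader might also infer that clinic contacts are counted twice, or that the ICER is therefore biased. The documents do not support this either. Register coding decides whether a double count exists at all, not merely how large it is, and the coding is not given. The Funding section says grants pay research staff, and nurse time has its own cost line. Both fit nurse support being additional to registry activity, though neither proves it. An omission would lower the intervention's cost and a double count would raise it, so the net direction of the two together is unknown.

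Two further limits stand. Minutes are not money: a share of nurse time does not translate into a share of total healthcare cost, and no passage ranks nurse time against the other costs that the intervention may change. The economic analysis is also secondary, and the Discussion already warns that the sample may be too small for it.

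**Conclusion.** The concern holds for telephone time, as a defect in the costing rule. As written, item (i) leaves out 0 to 180 min of nurse time per intervention patient, depending on how many of the nine interim contacts are by telephone. At the maximum this is 53% to 82% of scheduled nurse time; the range rests on the assumed nurse share of the quarterly visits, from the full 30 min down to none, and on scheduled rather than actual durations. The omission is one-sided: it understates the intervention's cost and favours it in the ICER, provided the registers do not price telephone contacts. The effect in money cannot be computed.

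On the registry overlap, the documents support only that reconciliation is not described and that double counting in the intervention arm is possible.

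The rule should be corrected before the economic analysis, particularly as the Discussion says the data analyst and health economist are not blinded. The point does not touch the primary outcome.

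**What to change.** **Telephone time.** Reword item (i) so that nurse time is costed at every intervention contact, clinic or telephone, using the consultation time log described in the source data section. State explicitly that the log includes calls.

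**Registry overlap.** Add a short rule to item (iii):
- Establish whether nurse contacts, in the clinic or by telephone, carry a registry tariff.
- Where they do, do not add nurse time that the tariff already covers.
- Treat nurse time in both arms by the same rule, including the possible 15 min at baseline in the non-intervention group.
- Report the incremental cost with and without the overlapping nurse time.

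Whole registry visit records should not be deleted by matching on patient and date. The dermatologist also attends the quarterly visits, so deletion could remove the dermatologist's cost from the intervention arm while the other arm keeps its tariffs.

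**Cost of the change.** A few sentences in the plan and a little more analysis work. The time log and the person-level register linkage are already planned. The intervention's cost will look less favourable where telephone use is common.
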